Appendix 5: Nicotine Patch Instructions

Read ALL the instructions before you begin.

Your abstinence period begins at 8pm, two days before your next NIDA visit (e.g., 8pm Saturday night if your visit is at 8am on Monday morning). Smoke a cigarette after dinner, before you commence the abstinence period, if this is usual for you. You will receive a phone call from a study investigator between 5pm and 8pm to ensure that you remember and understand the abstinence procedure. You will place the patch on as soon as you wake up the following day, that is, when you would typically have your first cigarette. To place and change the patch, follow the instructions outlined below. Do not smoke any cigarettes while you are wearing the patch. Since the nicotine patch works by delivering small doses of nicotine into the body, smoking may cause harmful levels of nicotine in your body.

How to apply the nicotine patch:

- 1. Do not remove the patch from its sealed protective pouch until you are ready to use it.
- 2. Choose a non-hairy, clean, dry area of skin. The upper arm is OK; we recommend the back where we will place the patch during the study. Do not put the patch on skin that is burned, broken out, cut, or irritated in any way. Make sure your skin is free of lotion and soap before applying the patch.
- 3. A clear, protective liner covers the sticky backside of the patch the side that will be put on your skin. The liner has a slit down the middle to help you remove it from the patch. With the sticky backside facing you, pull half the liner away from the patch starting at the middle slit, as shown in the illustration below. Hold the patch at one of the outside edges (touch the sticky side as little as possible), and pull off the other half of the protective liner.

4. Immediately apply the sticky side of the patch to your skin. Press the patch firmly on your skin with the palm of your hand for at least 10 seconds. Make sure it sticks well to your skin, especially around the edges. Mild itching, burning or tingling is normal and should go away within an hour.

- 5. Wash your hands after you apply the patch. Nicotine on your hands could get into your eyes and nose, and cause stinging, redness, or more serious problems.
- 6. After wearing the patch for 4 hours call the study nurses at **[contact]** to tell them how you are responding. If you do not call by 4:00 PM a member of the research team will contact you. Continue wearing the patch for the entire day and evening. Remove the patch just before you go to bed, the night before your NIDA visit.
- 7. On the morning of your NIDA visit, place a new patch on as soon as you wake up.

If your patch comes off during the day:

The patch generally sticks well to most people's skin. However, a patch may occasionally come off. If your patch falls off during your abstinence period, re-apply as soon as possible and hold in place with medical tape.

To prevent the patch from coming off, do not apply creams or lotions to the area on your skin where you will put the patch. Also, do not bathe, swim or shower during your test.

If you get a minor skin rash:

Use a topical salve (such as a hydrocortisone cream) around the patch.

If you experience any worrisome side effect from the patch (listed below):

Remove it at once and call **[name] [name] at [contact]**. **Also, the study nurses can be reached at [contact] (available 24 hours every day).**

Side effects of the nicotine patch include: dizziness, headache, upset stomach, vomiting, diarrhea, redness or swelling at the patch site.

Very rare serious side effects of the nicotine patch include: severe rash or swelling, seizures, abnormal heartbeat or rhythm, difficulty breathing.

Principal Investigator: [name].

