2.1. Primary goals

To characterize the neurobiological mechanisms underlying acute nicotine withdrawal and the maintenance of smoking behavior in current cigarette smokers. To achieve this, the current protocol will employ multiple task-based and resting state measures to probe the anhedonic and anxiogenic effects of acute nicotine withdrawal as well as reported inhibitory control deficits and increased impulsive decision-making. Changes in RSN dynamics will also be examined in relation to affective and cognitive symptoms associated with acute nicotine withdrawal. Acute nicotine-withdrawal will be manipulated by assessing dependent smokers twice: once in a non-deprived state (following 36 hours of smoking abstinence during which time they will continually wear a dose-matched nicotine patch) and on a second occasion in a nicotine-deprived state (following 36 hours of smoking abstinence whilst wearing a placebo patch). In the nicotine-deprived condition smokers are expected to report anhedonia and negative affective symptoms and associated changes in mesolimbic dopaminergic pathways

Principal Investigator: [name].

as well as amygdala and BNST functioning. As illustrated in Figure 1, we expect these changes to drive inhibitory control deficits and elevated impulsive decision making by altering functioning within and between intrinsic default mode, executive control and salience networks. Finally, the extent to which neurobiological changes resulting from acute nicotine withdrawal predict success of treatment for smoking cessation will be assessed.

Date: March 2, 2022

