- 4) Nicotine patch toleration test. Participants will complete a nicotine patch toleration test during the orientation visit. Nursing staff will apply the dose-matched nicotine patch at the end of the nurse assessment and will describe potential side effects to the participant. Participants will wear the patch for approximately 3 hours and will be asked to notify the LI or nursing staff immediately if they experience any worrisome side-effects. A nurse will remove the patch and conduct a post patch assessment including vital signs, neck/back pain assessment, mental status exam, and skin assessment.
- 3) Mock scanner training session. The mock scanner training session will familiarize participants with study procedures and the scanner environment. Given that training and scanning will take place on separate days, individuals will receive training refreshers during subsequent visits. ~ 1.5 hrs
- 5) Abstinence period procedure training. Participants will also be trained to measure their CO levels and record this using a small video camera. (see *Abstinence Periods* section for details). At the end of this visit they will generally also receive their first set of nicotine or placebo patches and will be instructed on the application of these during the abstinence periods as well as the time points and procedure for recording their CO and mood/withdrawal symptoms during their upcoming abstinence period. Subjects will also be provided with written instructions on how to apply each patch (see Appendix 5). CO monitors and video cameras and paper copies of self-report measures to complete during the abstinence period will also be distributed to participants at the end of their orientation session. Participants will also be provided instruction in cognitive behavioral techniques (e.g., progressive relaxation) designed to reduce withdrawal discomfort and improve compliance to the 36 hour abstinence procedure ~40min
- 6) Assessment of motivation and preparation to quit. Several measures assessing participant motivation and preparation to quit smoking (see Appendix 9) will be administered to the treatment-seeking smokers and those who enroll in the motivational arm. ~20min

Principal Investigator: [name].

(ii) Abstinence periods

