During both the nicotine-deprived and non-deprived abstinence period participants will use a small video camera to video record themselves measuring their CO levels. They will also report mood and withdrawal symptoms at 6 time points throughout each abstinence period: 10pm on day 1 (2hrs post-cessation); 8am on day 2 (12 hrs post-cessation); 12noon on day 2 (16 hrs post-cessation); 4pm on day 2 (20hrs post-cessation); 8pm on day 2 (24 hours post-cessation); 10pm on day 2 (26 hrs post-cessation). All times are approximate. Their CO levels will be measured again at 8am on day 3 (36 hrs post-abstinence) when they arrive at NIDA-IRP for their scanning session. Research staff will generally phone participants on the afternoon they are to commence their abstinence period. Participants may also receive text message reminders from research staff at each of the six measurement time-points depending on participant needs. This procedure will allow the research team to monitor participant CO levels throughout the 36 hr abstinence periods, validating smoking abstinence. It will also provide a method of measuring changes in mood and withdrawal symptoms throughout the 36 hr abstinence periods across both deprived and non-deprived conditions. This information will provide a measurement of responsivity to nicotine replacement.

Date: March 2, 2022

(iii) Scanning Visits.

There will be two scanning visits, both preceded by a 36 hr abstinence period. During one abstinence period and scanning session participants will wear a dose-matched nicotine patch. A placebo patch will be applied throughout the nicotine-deprived abstinence period and scanning session. The order of deprived and non-deprived sessions will be counterbalanced across subjects. Scanning sessions will be separated by a minimum of 5 days. The two scanning visits will be essentially identical. Each visit will consist of two 1.5 to 2 hr scanning sessions, one taking place in the morning (AM) and one in the afternoon (PM). Participants will also complete several preand post-scan tasks and a series of questionnaires throughout the day. All imaging visits will take approximately 9hrs (8am to 5pm) to complete. The order of procedures completed during each scan visit is outlined schematically in Figure 2, and described in detail below.

[figure not shown]

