9.1. Parameters to be monitored

Participants will complete a nicotine patch toleration test during the orientation visit. Nursing staff will apply the dose-matched nicotine patch at the end of the nurse assessment and will describe potential side effects to the participant. Participants will wear the patch for approximately 3 hours and will be asked to notify the LI or nursing staff immediately if they experience any worrisome side-effects.

Participants will be instructed during their orientation visit, and on the phone immediately prior to the commencement of each abstinence period, on the potential side effects of nicotine administration via transdermal patch. The details of what side effects are possible, when to remove the patch, and details of who to contact should participants experience side effects are clearly outlined in the Nicotine Patch Instructions (Appendix 5) which participants will take home with them from the orientation session. During telephone and in-person assessments participants will be directly asked open-ended questions will be used to assess for the presence of adverse effects. During placebo-patch and nicotine scans heart rates will be monitored via pulse oximeter. After completion of the scan, nursing will remove the patch and measure blood pressure and heart rate.

Based on Pfizer and FDA's ongoing safety review of post-marketing reports, Pfizer have modified the varenicline label in the U.S. to include a warning that patients who are attempting to quit smoking with varenicline should be observed for serious neuropsychiatric symptoms, including changes in behavior, agitation, depressed mood, suicidal ideation, and suicidal behavior. However, a recent cohort study based on the UK General Practice

Principal Investigator: [name].

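### Sections 2.1 and 4.4 describe patch wear over the whole 36 h abstinence, but Appendix 5 prescribes waking-hours wear from day 2, so the 10 pm day-1 home rating precedes any patch in both conditions

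*Combined protocol and SAP*

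**What the plan says.** Two places in the protocol body describe wear over the full abstinence. Section 2.1 defines the non-deprived state as "following 36 hours of smoking abstinence during which time they will continually wear a dose-matched nicotine patch". Section 4.4 (iii) says of the other condition: "A placebo patch will be applied throughout the nicotine-deprived abstinence period and scanning session".

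The detailed schedule is in Appendix 5. Abstinence starts at 8 pm, two days before an 8 am visit. For the first patch it says "You will place the patch on as soon as you wake up the following day". Step 6 then says "Remove the patch just before you go to bed, the night before your NIDA visit", and step 7 says "On the morning of your NIDA visit, place a new patch on as soon as you wake up".

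Appendix 5 is the written instruction that participants hold. Section 4.4 (i) gives it to them at orientation as the guide to applying each patch. Section 9.1 says that the possible side effects and when to remove the patch "are clearly outlined in the Nicotine Patch Instructions (Appendix 5) which participants will take home with them from the orientation session". Section 8.2 says the instructions are the same before the nicotine and the placebo period.

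Section 4.4 (ii) schedules six home ratings of mood and withdrawal: 10 pm on day 1, then 8 am, noon, 4 pm, 8 pm and 10 pm on day 2. It says this information will measure responsivity to nicotine replacement, which is a secondary goal in Section 2.2 and enters the correlational analyses of Section 11.2. The plan does not say how the six ratings are combined.

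**The concern.** The patch is the manipulation on which the main study rests, and the protocol describes its wear in two incompatible ways. Someone reporting the trial from Section 2.1 would call the contrast 36 h of continuous nicotine against none. Someone reporting it from Appendix 5 would call it nicotine patch against placebo patch during waking hours, within a 36 h smoking abstinence. These are different statements about what the non-deprived condition is.

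The second issue follows from the Appendix 5 clock. One of the six home ratings offered as a measure of responsivity is taken the evening before the first patch goes on. A difference between periods at that time reflects ordinary day-to-day variation in craving and mood, not nicotine. With no rule for summarising the ratings, an analyst could count it as outcome data, or overlook that it is a ready-made baseline.

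**Working it through.** **Inputs from the documents.** Abstinence runs from 8 pm on day 1 to 8 am on day 3 (Appendix 5; Section 4.4 (ii)). Patch on at waking on day 2, off at bedtime on day 2, on again at waking on day 3 (Appendix 5). Ratings as listed in Section 4.4 (ii).

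**Inputs assumed.** The documents give no sleep times. I take waking at 5 to 8 am and bedtime at 10 pm to midnight, the same each day.

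**Step 1: the plan's own timeline.** 8 pm on day 1 to 8 am on day 3 is 4 + 24 + 8 = 36 h. Counted from 8 pm, the ratings fall at 2, 12, 16, 20, 24 and 26 h. Both agree with Section 4.4 (ii).

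**Step 2: hours off patch.** Let *w* be the waking hour and *b* the bedtime hour on a 24 h clock.

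- First gap, 8 pm on day 1 to waking on day 2: 4 + *w*.
- Second gap, bedtime on day 2 to waking on day 3: (24 − *b*) + *w*.
- Total: 28 + 2*w* − *b*.
- Shortest (*w* = 5, *b* = 24): 28 + 10 − 24 = 14 h, or 14/36 = 39%.
- Longest (*w* = 8, *b* = 22): 28 + 16 − 22 = 22 h, or 22/36 = 61%.
- Waking at 7 am, bed at 11 pm: 28 + 14 − 23 = 19 h, or 53%.

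Waking at 8 am on day 3 is an outer limit, since that is the arrival time. With waking by 7 am that day the maximum is 21 h. Sections 2.1 and 4.4 (iii) imply 0 h off patch.

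**Step 3: how much of the gap is waking time.** Only the first evening, 8 pm to bedtime: *b* − 20 = 2 to 4 h. The rest, 2(24 − *b* + *w*), is night: 10 h in the shortest case, 20 h in the longest, and 16 of 19 h in the 7 am and 11 pm case.

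**Step 4: each rating relative to the first patch** (applied 9 to 12 h after 8 pm):

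- 10 pm day 1: 7 to 10 h before
- 8 am day 2: 0 to 3 h after
- Noon: 4 to 7 h after
- 4 pm: 8 to 11 h after
- 8 pm: 12 to 15 h after
- 10 pm day 2: 14 to 17 h after

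The first line's sign does not depend on the assumed times: 10 pm on day 1 always precedes waking on day 2.

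**Step 5: the scan day.** The new patch has been on 0 to 3 h at 8 am arrival. Nurse assessment (30 min), task practice (30), EEG preparation (45) and scanner set-up (15) add about 2 h, so the morning scan starts about 2 to 5 h after application. Section 24.6 uses a 2 h lead in the tDCS arm.

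**Step 6: power.** A two-sided paired t-test at d = 0.5, α = 0.05 and power 0.80 needs 34 participants, against about 35 in Section 11.4. Patch-wear hours do not enter that calculation.

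**The case against.** The strongest reply is that this is loose wording in two sentences. Elsewhere the protocol says only that a patch is worn, or nicotine delivered, during the abstinence period, which is compatible with Appendix 5. Waking-hours wear looks deliberate: Appendix 5 ties application to the usual time of the first cigarette, and Section 4.1 aims to match daily intake. That stands, and I do not criticise the wear schedule itself. But the two sentences do conflict with Appendix 5, and nothing reconciles them.

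Nor do the documents say which text governs. Participants also receive training and telephone instructions whose content on patch timing is not shown. Section 8.2 calls the product a 24 h patch, and Section 1.7 aims to keep withdrawal low in the non-deprived condition. So a reader might infer that the stated exposure is demonstrably not the one delivered. The documents support less: the written instruction differs from the stated exposure, and either text could be the one to amend.

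Section 4.4 (ii) can also be read as describing a time course, in which a pre-patch starting point is useful. That is fair, and it is the role proposed under the fix. The plan does not assign it. Responsivity in Section 2.2 is not limited to home ratings either; symptoms are also rated on the scan day with the patch on.

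**Conclusion.** The point holds and is minor. The protocol contains two incompatible descriptions of patch wear. If Appendix 5 is followed, the patch is off for roughly 14 to 22 of 36 h in both conditions, mostly overnight, with 2 to 4 h of waking time on the first evening. Those hours rest on assumed sleep times. That the 10 pm day-1 rating is pre-patch rests only on Appendix 5 being followed.

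Two stronger readings are not supported. A reader might infer that the home-rating contrast shrinks to five sixths of its true size because one of six ratings carries no effect. That needs an equal-weight mean of all six, which the plan never proposes, and a constant difference at the other five, which is doubtful when time on patch runs from 0–3 h to 14–17 h. It is not an expected effect. A reader might also infer that the main comparison is compromised. It is not: the schedule is the same for both patches, the patch is on during scanning, and plasma nicotine is sampled on the scan day. Blinding, the scan-day contrast, sample size and power stand.

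**What to change.** 1. Make the texts agree. If Appendix 5 is the intended schedule, correct Sections 2.1 and 4.4 (iii) and describe the contrast as waking-hours nicotine versus placebo patch over a 36 h smoking abstinence. If continuous wear is intended, amend Appendix 5.

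2. With the Appendix 5 schedule, define home-rating responsivity from the five post-application ratings and exclude the 10 pm day-1 rating from that outcome. Use that rating as the period-specific baseline. It differs between periods, so the one-way repeated-measures ANCOVA of Section 11.2 does not take it directly. Two forms work:
   - Regress D on B and nicotine dose, where D is the placebo-minus-nicotine difference in the five-rating summary and B is the same difference at 10 pm on day 1.
   - Fit a mixed model with the 10 pm rating as a period-level covariate.

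Optional: a sensitivity analysis that omits the 8 am day-2 rating for everyone, and a note of patch application time on the take-home form or at the existing 4-hour nurse call.

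Cost: wording changes in two sections (or one appendix) and one analysis rule, with a small change of model for the home ratings. No new visits, assessments or participants.

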Appendix 6: Coping strategies

Methods to help you cope with smoking withdrawal symptoms

1. Reminding yourself of the positive consequences of not smoking (such as improved health and appearance, feelings of success and self-control, monetary savings) as well as the negative consequences of smoking (e.g., such as the smell on clothing, hands and breath, negative health consequences).

Exercise

Make a list of reasons you want to quit smoking. Try not to only come up with negative consequences to be avoided, but also benefits to be made. From this list, pick the number 1 reason you want to quit smoking. This can function as a simple internal message of encouragement when you are finding the abstinence period difficult.

spending time with nonsmoking friends, going to the movies, taking long walks, cooking.

- 3. Keep your hands active. Some smokers miss the tactile sensation of holding a cigarette. Find something you can hold and manipulate to help with this. Manipulating a stress ball or just a pen or pencil can help relieve the desire to hold a cigarette.
- 4. Have healthy snacks on hand. You may find that your appetite increases when you stop smoking. Having healthy snacks available (e.g., carrot or celery sticks, sugarless candie or chewing gum not nicotine gum) will help with this. Also, instead of taking a cigarette break, take a break and have a snack instead.
- 5. Relaxation. Feeling tense or stressed will make it even more difficult for you to stop smoking. We have provided you with a 10min progressive muscle relaxation guide that you can use to help reduce tension, relieve stress and help you relax. Try doing this 10 min relaxation tape when you are feeling particularly tense/stressed or particularly strong desire to smoke.

Here are some progressive relaxation videos you can follow:

http://www.youtube.com/watch?v=HFwCKKa--18

http://www.youtube.com/watch?v=PYsuvRNZfxE

http://www.youtube.com/watch?v=KmxfjjamcuY

Appendix 7: Varenicline Toleration Assessment

After participants start varenicline, a masters level therapist, LI, or study clinician will conduct a semi-structured interview to assess toleration of varenicline. The assessment will be conducted weekly, either in person or via phone, while participants are taking varenicline, and for two weeks after their last dose. The therapist will be extensively trained by the MAI on question administration. If the interview reveals a possibility of significant side effects, the participant will be put in contact with the MAI for further evaluation. The MAI will decide whether study pill administration needs to be discontinued and other action taken based on the severity of the symptoms.

- 1) Since we last spoke or met, how have you been feeling? (open-ended question)
- 2) Have you noticed any physical side effects [or, a change in the severity of any physical side effects], such as nausea, vomiting, dizziness, or headache? Anything else?
- 3) Have you noticed a change in behavior that would be considered out of the ordinary for you?
 - 4) Do you feel more restless, wound-up, or agitated than usual?
 - 5) Do you feel more irritable or cranky than usual?
- 6) Have you noticed an increase in feelings of depression, such as sadness, hopelessness, helplessness or worthlessness?
- 8) Have you had thoughts of violence towards others? ...acted aggressively towards someone?
- 7) Have you had thoughts of death? ...wished you were dead? ...had thoughts of killing yourself?

Participants will also be reminded to call if any issues should arise between assessments.

Principal Investigator: [name].

